10.3 Assessment of severity

The severity of adverse events will be assessed according to scales based on FDA toxicity grading scales for healthy adult volunteers enrolled in preventive vaccine clinical trials, listed in the table below.

Severity grade	Assessment criteria
----------------	---------------------

**University of
Nottingham**
Health Service

Grade 1	Mild: Transient or mild discomfort (< 48 hours); No interference with activity; No medical intervention/therapy required
Grade 2	Moderate: Mild to moderate limitation in activity – some assistance may be needed; no or minimal medical intervention/therapy required
Grade 3	Severe: Marked limitation in activity, some assistance usually required; medical intervention/therapy required.
Grade 4	Potentially Life-threatening: requires assessment in A&E or hospitalisation

10.4 Safety reporting procedures

SAEs and AESIs will be reported to the CI as soon as possible after being reported to a member of the team. The CI will be responsible for deciding whether the participant is able to continue the study; whether the study can continue; and whether the sponsor should be informed.

Assignments of causality will only be made in relation to the administration of Vitamin D and/or positive mood intervention during the study. Any SAEs which occur following externally administered vaccines or medicines e.g., those given as part of the patient's usual care, will be judged to be unrelated to the study vaccine and should additionally be reported through national pharmacovigilance mechanisms as applicable.

Hospitalisation (including inpatient or outpatient hospitalisation for an elective procedure) for a pre-existing (existing prior to administration of Vitamin D during the study) condition that has not worsened unexpectedly does not constitute an SAE. Emergency department attendances should not routinely be reported as SAEs unless they meet the SAE definition described above.

The procedure for reporting of Serious Adverse Events is to complete an SAE report form for all reportable SAEs. The CI or delegate will submit (in addition to the expedited reporting above) DSURs once a year throughout the clinical trial, or on request, to the Competent Authority (MHRA), Ethics Committee, HRA (where required), Host NHS Trust and Sponsor. The safety profile will be continuously assessed by the Investigators. The CI and relevant investigators (according to the study delegation record) will also review safety and SAE issues as they arise.

**University of
Nottingham**
Health Service

11. Statistics

Evaluation of the findings will be conducted by the study team using SPSS and overseen by the study statistician [name].

The main statistical analysis will be to identify a statistically significant difference in the four groups and identify any additional immune effect of vitamin D supplementation given at the time of vaccination. We will use a range of advanced techniques, such as multivariate statistical methods and advanced clustering and classification approaches to assess the independent and combined contribution of psycho-behavioural factors to immunological responses to the vaccination.

All validated measures employed will be summarised according to published guidelines.

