10.1 Adverse event definitions

Adverse Event (AE)	Any untoward medical occurrence in a participant to whom a medicinal product has been administered, including occurrences which are not necessarily caused by or related to that product.
Adverse Reaction (AR)	An untoward and unintended response in a participant to an investigational medicinal product which is related to any dose administered to that participant. The phrase "response to an investigational medicinal product" means that a causal relationship between a trial medication and an AE is at least a reasonable possibility, i.e., the relationship cannot be ruled out. All cases judged by either the reporting medically qualified professional or the Sponsor as having a reasonable suspected causal relationship to the trial medication qualify as adverse reactions.

**University of
Nottingham**
Health Service

Serious Adverse Event (SAE)
	
A serious adverse event is any untoward medical occurrence that:
 
 • results in death • is life-threatening • requires inpatient hospitalisation or prolongation of existing hospitalisation • results in persistent or significant disability/incapacity • consists of a congenital anomaly or birth defect*. 
Other 'important medical events' may also be considered a serious adverse event when, based upon appropriate medical judgement, the event may jeopardise the participant and may require medical or surgical intervention to prevent one of the outcomes listed above.
 
NOTE: The term "life-threatening" in the definition of "serious" refers to an event in which the participant was at risk of death at the time of the event; it does not refer to an event which hypothetically might have caused death if it were more severe.
 
NOTE: Pregnancy is not, in itself an SAE, but an adverse outcome of pregnancy, for example spontaneous miscarriage, may be judged to be an SAE if clinically appropriate.

Serious Adverse Reaction (SAR)
	
An adverse event that is both serious and, in the opinion of the reporting Investigator, believed with reasonable probability to be due to one of the trial treatments, based on the information provided.

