
Suspected Unexpected Serious Adverse Reaction (SUSAR)
	
A serious adverse reaction, the nature and severity of which is not consistent with the Reference Safety Information for the medicinal product in question set out:
 
 • in the case of a product with a marketing authorisation, in the approved summary of product characteristics (SmPC) for that product • in the case of any other investigational medicinal product, in the approved investigator's brochure (IB) relating to the trial in question.

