10.2 Assessment of causality

**University of
Nottingham**
Health Service

Causality will be clinically assessed relative to the interventions administered during the trial by the Chief Investigator. An adverse event is considered to have a causal relationship to an intervention if the attribution is possible, probable, or very likely by the definitions listed below. An adverse event is considered to have no causal relationship to an intervention if the attribution is not related or unlikely by the definitions listed below. In the group receiving two interventions, the attribution of any adverse event to either of the individual interventions will be at the Chief Investigator’s discretion.

Causality term	Assessment criteria
0 No relationship	No temporal relationship to study product and Alternate aetiology (clinical state, environmental or other interventions); and Does not follow known pattern of response to study product
1 Unlikely	Unlikely temporal relationship to study product and Alternate aetiology likely (clinical state, environmental or other interventions) and Does not follow known typical or plausible pattern of response to study product.
2 Possible	Reasonable temporal relationship to study product; or Event not readily produced by clinical state, environmental or other interventions; or Similar pattern of response to that seen with other vaccines
3 Probable	Reasonable temporal relationship to study product; and Event not readily produced by clinical state, environment, or other interventions or Known pattern of response seen with other vaccines
4 Definite	Reasonable temporal relationship to study product; and Event not readily produced by clinical state, environment, or other interventions; and Known pattern of response seen with other vaccines

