Any deviations will be documented in a protocol deviation form and filed in the ISF. Each deviation will be assessed as to its impact on participant safety and study conduct. Significant protocol deviations will be listed in the end of study report.

A serious breach is defined as “A breach of GCP or the trial protocol which is likely to affect to a significant degree –

- (a) the safety or physical or mental integrity of the subjects of the trial; or
- (b) the scientific value of the trial.”

In the event that a serious breach is suspected the Sponsor must be contacted within 1 working day. In collaboration with the CI the serious breach will be reviewed by the Sponsor and, if appropriate, the Sponsor will report it to the REC committee, Regulatory authority and the relevant NHS host organisation within seven calendar days.

**University of
Nottingham**
Health Service

15. Ethical and regulatory considerations

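### Section 10.4 makes telling the Sponsor of an SAE discretionary and cites an absent expedited procedure, so the Sponsor's causality judgement in 10.1 is not assured and SUSARs have no reporting route

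*Protocol*

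**What the plan says.** Section 10.4 makes the CI the recipient of serious events: "SAEs and AESIs will be reported to the CI as soon as possible after being reported to a member of the team". It then gives the CI three decisions: whether the participant stays in, "whether the study can continue; and whether the sponsor should be informed". The section asks for an SAE form for each reportable SAE but names neither a recipient nor a deadline. It adds a yearly (or on request) safety update report, whose recipients include the Sponsor, and describes that report as coming "in addition to the expedited reporting above".

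Section 10.1 defines the event classes:

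- Adverse reaction row: "All cases judged by either the reporting medically qualified professional or the Sponsor as having a reasonable suspected causal relationship" count as adverse reactions.
- Serious adverse reaction (SAR) row: an event that is serious and, "in the opinion of the reporting Investigator, believed with reasonable probability to be due to one of the trial treatments".
- SUSAR row: a serious adverse reaction, "the nature and severity of which is not consistent with the Reference Safety Information for the medicinal product in question".

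Section 10.2 assigns the assessment: "Causality will be clinically assessed relative to the interventions administered during the trial by the Chief Investigator". In the arm with two interventions, attribution between them is also at the CI's discretion.

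Section 14 covers a different kind of event: "In the event that a serious breach is suspected the Sponsor must be contacted within 1 working day".

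**The concern.** The adverse reaction definition gives the Sponsor a judgement of its own: a case counts if either party suspects a link. That safeguard matters most when the investigator side sees no link and the Sponsor might. To exercise it, the Sponsor has to know that the event occurred. Section 10.4 makes that knowledge depend on a choice by the CI, who is also the named causality assessor.

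This is a rule written into the protocol, not a detail left for another document. A site that followed it to the letter could leave the Sponsor unaware of an individual SAE, a death included, and commit no deviation. At stake is the Sponsor's oversight of safety in participants aged 65 and over, including during the period when the steering group may let recruitment resume (section 11.1). That group consists of the investigators and the study co-ordinator, and the criteria listed for its decision concern acceptability and adherence data.

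**Working it through.** The plan gives no figure to reproduce. The check is to follow one SAE through the text.

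1. **Event to CI.** A team member hears of the SAE and it goes to the CI as soon as possible (10.4). Nothing is wrong here.
2. **Causality.** The CI assesses it (10.2). Suppose the result is one of the two lowest categories, which 10.2 treats as no causal relationship.
3. **CI to Sponsor.** Section 10.4 lets the CI decide. There is no criterion, so either choice complies. The discretion is not limited to unrelated events, but this is the case in which a second view could change the classification.
4. **Sponsor's view.** The adverse reaction row in 10.1 allows the Sponsor to disagree. If step 3 ended without notice, there is no event in front of the Sponsor to judge.
5. **SUSAR.** If an event is classed as a SUSAR, the next instruction should say who reports it, to whom and by when. The 10.1 entry is a definition with no actor, action or deadline. Section 10.4 refers back to expedited reporting, but nothing from the opening of section 10 to that sentence describes any.

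The protocol also gives three accounts of who judges causality:

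| Place | Who judges |
|---|---|
| 10.1, adverse reaction row | Reporting medically qualified professional or Sponsor |
| 10.1, SAR row | Reporting investigator |
| 10.2 | CI |

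Other routes by which the Sponsor could learn of the event:

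| Route | Does it guarantee prompt notice of one SAE? |
|---|---|
| SAE form (10.4) | No: no recipient or deadline stated |
| Safety update report (10.4) | No: yearly or on request |
| Annual progress report (15.5) | No: yearly or on request |
| Monitoring, audit and record access (12) | No: a right to look, not a duty to tell |
| GCP, regulations and SOPs (13, 15.2) | No: general references that leave the written discretion in place |

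None of the five closes the gap left by step 3.

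**Illustration of workload only.** The protocol gives no SAE rate. Assume 10 to 30 unplanned admissions per 100 person-years, and follow-up of 168 days (section 10).

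- 40 participants: 40 × 168/365 = 18.4 person-years; × 0.10 to 0.30 = 1.8 to 5.5 events.
- 80 participants: 80 × 168/365 = 36.8 person-years; × 0.10 to 0.30 = 3.7 to 11.0 events.

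This suggests that few forms would need forwarding. It does not measure harm: it counts all admissions, not related events that were misjudged. The point does not depend on it.

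**The case against.** The strongest reply is that the Sponsor is not cut off and the CI does not act alone. Events reach a team member before the CI, the CI and relevant investigators review SAE issues as they arise, and primary care records are reviewed at 28 and 168 days. The Sponsor may ask for a safety update report at any time and may inspect records. The interventions look low risk, and neither the feasibility objective, the randomisation nor the analysis is affected.

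Most of this is correct, and it rules out several stronger readings that a reader might infer:

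- *That the CI can keep an SAE from everyone.* Section 10.4 shows that other team members and investigators see these events. The discretion concerns onward notice to the Sponsor.
- *That the Sponsor's judgement cannot work at all.* It works whenever the CI chooses to inform. The defect is that nothing assures this.
- *That 10.4 disables a SUSAR step in 10.1.* There is no such step. The SAR row rests on the reporting investigator's opinion and expectedness on the Reference Safety Information, so an event can be classed as a SUSAR without the Sponsor. What is absent is the route onward.
- *That the Sponsor must wait 12 months.* The report is also available on request, and access rights exist.
- *That the either/or rule runs through all of 10.1.* It stands in the adverse reaction row only; the SAR row omits the Sponsor.

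The reply does not remove the core. A request or an inspection helps little if the Sponsor has no reason to suspect an event, and general references to SOPs and GCP do not cancel an explicit discretion.

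**Conclusion.** The point holds as a conflict within the safety section. Sponsor notification of an SAE is discretionary, without criterion or time limit. The Sponsor's judgement under the adverse reaction definition is consequently not assured for SAEs that the CI considers unrelated. SUSARs are defined but lead nowhere, because the expedited procedure referred to is absent from section 10.

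The size is procedural, not numerical. Every SAE in the trial falls under the discretion, and section 10 guarantees the Sponsor only periodic or requested reports. The 1-working-day rule in section 14 shows that the protocol can set a firm duty to contact the Sponsor, but it governs serious breaches, and nothing shows that it was meant for SAEs. The conclusion assumes only that the protocol is followed as written and that no other protocol text imposes prompt notice; none was found. It does not imply that any event has been or would be withheld. Because it concerns safety oversight and costs almost nothing to correct, it should be corrected.

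**What to change.** - In 10.4, delete the CI's decision on whether to inform the Sponsor. State that every SAE form goes to the Sponsor within a fixed time of site awareness, whatever the CI's view of causality. The Sponsor should set the limit; the interval in section 14 is a reference point only.
- Reconcile the adverse reaction and SAR rows of 10.1 with 10.2 and 10.4, so that one rule says who judges causality. If the Sponsor keeps an independent judgement, say that it applies to serious events, that it is recorded, and what follows when the two views differ.
- Replace the reference to expedited reporting with the actual SUSAR route (who reports, to whom, by when), or delete it if that route is set out elsewhere and cite the place.

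The cost is a wording amendment and the forwarding of a small number of forms that 10.4 already requires. No new visits or data collection are needed; the Sponsor would spend some time recording its view.

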18.	Development of a new product/process or the generation of intellectual property	31
19.	References	32
20.	Appendices	34
20.1	Vitamin D Supplementation	34

**University of
Nottingham**
Health Service

3. Plain English Summary

Vaccines help us prevent diseases and keep us well. Some vaccines work better than others and there are many reasons for this. It can be to do with the vaccine itself or to do with the person having the vaccine. We have already found that people who report feeling happier on the day they are vaccinated produce more antibodies in response to the vaccination. We have also found that giving people only 15 minutes of a positive mood intervention to watch before they are vaccinated improves their mood. Recent research also suggests that the amount of vitamin D in your body at the time of vaccination can affect how well vaccines work.

In this study we will conduct a small experiment in which people who are about to receive a COVID-19 or influenza vaccination, or both, will be put in one of 4 groups at random.

- Group 1 will not be offered anything other than their vaccine (this is called usual care).
- Group 2 will receive a brief positive mood intervention, which has previously been shown to improve mood on the day they are vaccinated and for a further 6 days. They will also be advised to take a single dose of a vitamin D tablet just before they are vaccinated and once daily for the following 27 days.
- Group 3 will also receive the positive mood intervention on the day they are vaccinated and for a further 6 days, but they will not take the vitamin D tablet.
- Group 4 will be advised to take a vitamin D tablet at the time of vaccination and once daily for the following 27 days.

We will ask all participants to provide 15ml blood samples before vaccination and then at 28 days and at 6 months post vaccination. This sample will help us measure antibody responses to the vaccination and determine how well people have responded. In addition, up to 20 people across all groups will be asked to provide up to a 60ml blood sample at baseline and at day 28. These samples will allow us to understand how our interventions are changing the way the immune system works.

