UNHS:	University of Nottingham Health Service

**University of
Nottingham**
Health Service

6. Background and rationale

Vaccines play a critical role in reducing the burden of infectious disease in the population. However, with all vaccines there is variability in the effectiveness and durability of protection, with the greatest variability evident in older people. Previous research has shown that a range of emotional and lifestyle factors alter vaccine effectiveness including positive and negative mood^{1,2} and vitamin D status³ and that interventions which target these factors can enhance vaccine success⁴. Furthermore, there is evidence that vitamin D and negative mood may be inversely related, suggesting that an intervention which combines both adjuvants may have synergistic effects.

The proposed project would build on existing evidence which has demonstrated the benefits of positive mood and vitamin D for vaccine effectiveness. The aims would be to:

1. Adapt an existing brief single session positive mood intervention to permit delivery of multiple sessions in the seven days post-vaccination
2. Assess the feasibility and acceptability of vitamin D supplementation for 28 days and a brief positive mood intervention for 7 days in older adults.
3. Gather preliminary evidence on the effects of positive mood alone, vitamin D alone and positive mood and vitamin D in combination on the antibody response to influenza and SARS-CoV-2 virus vaccines
4. Investigate the cellular and humoral immune mechanisms mediating intervention effects

**University of
Nottingham**
Health Service

7. Methods

Patients aged 65 years or greater being targeted for COVID-19 and/or influenza vaccination will be recruited from primary care to participate in a feasibility trial. They will be randomly allocated on a 1:1:1:1 basis to receive:

- No intervention (Usual Care)
- Positive mood intervention on the day of vaccination and for the following 6 days and vitamin D supplementation on the day of vaccination and once daily for the following 27 days
- Positive mood intervention on the day of vaccination and for the following 6 days
- Single dose oral vitamin D supplementation on the day of vaccination and once daily for the following 27 days

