15 ml venous blood samples will be collected to detect antibodies to the vaccine antigens. These will be measured at baseline, 4 weeks and 6 months post-vaccine to assess intervention effects on peak vaccine responses and durability of protection. Participants will also receive a daily text message reminder with a link to the positive mood intervention and/or to take their vitamin D supplement, alongside an e-diary link to complete.

A sub-sample of up to 20 patients will be invited to have blood samples collected to explore potential cellular and humoral mechanisms at day 0 and day 28. This will entail an additional maximum 60ml blood sample on each occasion.

Interviews will be conducted with patients and health care professionals involved in the pilot trial to identify barriers and facilitators to implementing the intervention in routine care.

8. Participant identification

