9.2 Informed consent and enrolment

Patients invited for their COVID-19 booster vaccination and/or influenza vaccination as part of the national vaccine schedule that fit all other eligibility criteria will be invited to take part in the study.

The participant will have had sufficient opportunity, a minimum of 24 hours, to read and understand the contents of the PIS prior to being invited to provide informed consent, with further opportunities to ask questions and seek clarification at the consent and enrolment visit.

Each participant must give informed consent for the study and will be asked to acknowledge having read the latest approved version of the PIS and ICF before any study specific procedures are performed. Consent, randomisation, and vaccination will occur on visit 1. This will include consent, baseline blood collection, intervention administration and vaccination. The visit is not expected to take more than 60 minutes in total.

The PIS and ICF will present no less than the following information to the participant:

- The nature of and rationale for performing the study
- Implications and constraints of the protocol
- The risks and benefits involved in taking part in the trial

It will be clearly stated that there will be no provisions to supply participants with individual blood test results at any time, that the participant is free to withdraw from the study at any time, for any reason and that they are under no obligation to give the reason for withdrawal.

After giving informed consent participants will be allocated a unique study number.

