9.4 Subsequent visits

**University of
Nottingham**
Health Service

At day 28 and 168 after visit 1, participants will be asked to provide a further 15ml blood sample to measure immunological and biochemical responses.

Participants in the optional immunology subgroup cohort may be invited to have a larger blood sample (up to 60ml) collected at day 28.

A qualitative nested interview study will be used to assess participants', clinicians' and other stakeholders' views on intervention and trial acceptability and determine the barriers and facilitators to implementing the intervention in routine care. The process for obtaining participant informed consent for the study will include consent for potential inclusion in the qualitative interview nested study. The qualitative study will be reported in line with the Consolidated Criteria for Reporting Qualitative Research (COREQ: Tong et al, 2007).

We will conduct semi-structured interviews with a sample of patient participants and stakeholders (healthcare professionals, or other practice staff involved in explaining the trial to patients, conducting the screening and consent processes, or delivering the intervention). We aim to complete these within 4 weeks of the end of the intervention period. Interviews will be conducted by telephone, video call or face-to-face at participant preference, audio-recorded (with permission) and transcribed verbatim. Topic guides will be developed based on study aims and input from the Trial Management Group (TMG). Interview participants will be selected purposively to ensure diversity in relevant characteristics (e.g., trial group allocation, age, gender, ethnicity, deprivation index, region). Sampling will cease when we have sufficient information power relevant to the study aims (Malterud et al, 2016) although we anticipate up to 20 participants, and 10 stakeholders. Analysis of qualitative data will use appropriate methods such as inductive thematic analysis.

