9.9 Definition of end of study

The end of the study will be defined as the time the last blood sample is analysed.

10. Safety reporting

Safety reporting for participants in this study begins at the point of consent and ends at 168 days post-enrolment. Safety data will be collected via:

- Direct notification by the participant to the investigator via email or telephone according to the information on the study contact card given to each participant at enrolment.
- Investigator review of primary care medical records at 28 days and 168 days.

All serious adverse events that have not resolved by the end of the study, or that have not resolved upon discontinuation of a subject's participation in the study, must be followed until any of the following occurs:

- The event resolves
- The event stabilises
- The event returns to a baseline if a baseline value is available
- The event can be attributed to agents other than to study interventions or to factors unrelated to study conduct
- It becomes unlikely that any additional information can be obtained (participant or health care practitioner refusal to provide additional information, lost to follow-up after demonstration of due diligence with follow-up efforts)

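### Section 10.4 limits causality to vitamin D and the mood intervention, so harm from a study blood draw can be recorded but not as related to the trial

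*Protocol*

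**What the plan says.** **Causality.** Protocol section 10.4 sets the scope: "Assignments of causality will only be made in relation to the administration of Vitamin D and/or positive mood intervention during the study". Section 10.2 is consistent with it: "Causality will be clinically assessed relative to the interventions administered during the trial by the Chief Investigator". The grade table in 10.2 words its criteria in terms of a study product, and its upper grades compare the event with what is seen after other vaccines.

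**Definitions (10.1).** An adverse event is defined for a participant who has been given a medicinal product. An adverse reaction is a response to an investigational medicinal product. A serious adverse reaction must be thought due to one of the trial treatments. None of these mentions study procedures.

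**Blood sampling.** The plain English summary says: "We will ask all participants to provide 15ml blood samples before vaccination and then at 28 days and at 6 months post vaccination". Section 9.4 repeats the follow-up samples: "At day 28 and 168 after visit 1, participants will be asked to provide a further 15ml blood sample". For a sub-sample of up to 20 people at day 0 and day 28, section 7 adds: "This will entail an additional maximum 60ml blood sample on each occasion". Section 8.3 excludes people for whom blood collection is contraindicated.

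**Collection of safety data.** Section 10 runs from consent to day 168, by participant notification and by review of primary care records at days 28 and 168. Under 10.4, SAEs and AESIs go to the chief investigator.

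**The concern.** The study draws are research procedures that participants undergo only because they joined the trial. They are given to people aged 65 and over in all four arms. Section 8.3 already treats sampling as something that can be unsafe for some people, and the safety window covers every draw.

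The word *only* in 10.4 closes the list of possible causes at two, and sampling is not one of them. An investigator who sees a haematoma, or a faint with a fall, after a study draw can report the event but has no category in which to say that the trial caused it. Usual care shows this most clearly: those participants are bled on the same schedule and receive neither listed cause.

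What is at stake is the accuracy of the relatedness label in the safety tables. Anyone reading related events by arm would see nothing for usual care, and nothing for sampling in any arm, whatever had happened.

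**Working it through.** There is no figure in the plan to reproduce. The check is a comparison of the sections, followed by a count of the draws.

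**Step 1: is there any route to a procedure-related label?**

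| Place | What it ties causality to | Covers a blood draw? |
|---|---|---|
| 10.1, adverse reaction | investigational medicinal product | No |
| 10.1, serious adverse reaction | trial treatments | No |
| 10.2, opening text | interventions given in the trial | No |
| 10.2, grade table | study product; pattern seen with other vaccines | No |
| 10.4 | vitamin D and/or mood intervention, exclusively | No |
| 9.8, withdrawal | mentions adverse events that require study procedures to stop | Assigns no cause |
| 10, end of SAE follow-up | mentions study conduct | Assigns no grade |

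No section supplies the category.

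**Step 2: two cases.**
- *Usual care.* The arm receives neither vitamin D nor the mood intervention. Under 10.4 no event in it can be graded as related.
- *Baseline draw, any arm.* Section 9.2 describes visit 1 as follows: "This will include consent, baseline blood collection, intervention administration and vaccination". If events follow the listed order, an injury from the baseline draw comes before the intervention and cannot be graded as related to it.

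**Step 3: how many draws are exposed to the gap.** Inputs: three routine draws per participant (plain English summary; 9.3 and 9.4); a minimum of 10 per arm, about 40 in total, or a minimum of 20 per arm, about 80 in total, if recruitment resumes (11.1); a subgroup of up to 20 people sampled twice (7). Complete follow-up is assumed.

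| | About 40 participants | About 80 participants |
|---|---|---|
| All routine draws | 3 × 40 = 120 | 3 × 80 = 240 |
| Of which usual care | 3 × 10 = 30 | 3 × 20 = 60 |
| Subgroup samples of up to 60 ml | up to 2 × 20 = 40 | up to 2 × 20 = 40 |

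The subgroup samples fall at the same day 0 and day 28 visits. They are listed separately and not added to the totals.

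**Step 4: what cannot be computed.** The protocol gives no complication rate for venous sampling, for any event or for serious ones, so no expected number of mislabelled events follows from it. The gap does not depend on a rate: whatever the rate, none of these events can be labelled related to a study procedure.

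**The case against.** The strongest reply is that nothing is lost except a label. Data collection in section 10 does not depend on causality. Section 10.4 sends all SAEs to the chief investigator, who decides on continuation and on informing the sponsor without relatedness being a condition. Section 10.2 says only that an event has no causal relationship to an intervention, which is true of a bruise from a needle. This stands, and it limits the point to attribution. The one qualification is that the AE definition in 10.1 presupposes a medicinal product. Usual care and mood-only participants receive none from the study, so the definition fits them poorly even though the collection procedures include them.

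Four stronger readings are tempting, and the document does not support them.

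- *That the sections contradict each other.* Section 10 allows follow-up of an unresolved SAE to end on this ground, among others: "The event can be attributed to agents other than to study interventions or to factors unrelated to study conduct". That is an end point for follow-up and not a causality category. It can stand beside 10.4.
- *That a serious draw injury would miss a reporting step.* Section 10.1 defines a serious adverse reaction, but 10.4 describes no separate step that such an event would fail to reach.
- *That draw injuries would be attributed to mood.* This conflicts with the restriction itself, and the lower grades in 10.2 point to alternative causes, including other interventions.
- *That a false zero would enter the design of the next trial.* Section 11.1 ties the decision on whether the data suffice to acceptability and to adherence capture. The synopsis lists no safety outcome, and no section says that a procedure-harm rate will be carried forward.

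**Conclusion.** The point holds as a gap in the scope of causality assessment. As written, an adverse event caused by a study blood draw can be recorded as an AE or SAE but not as related to the trial, and in usual care no event of any kind can be graded as related. The gap covers about 120 routine draws in 40 participants, about 30 of them in usual care (about 240 and 60 if recruitment goes on to 80), as well as the larger subgroup samples. These counts assume complete follow-up and the minimum number per arm.

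Confidence is high on the restriction and on the absence of any other route, since both rest on the text alone. How many events would be mislabelled cannot be stated from the protocol. The point concerns safety attribution only and has no bearing on the sample size, the primary feasibility objective or the exploratory antibody analyses. It merits correction because the remedy is cheap and the scope is fixed in the protocol's own safety section, so it is not a detail left for an analysis plan.

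**What to change.** Three linked wording changes:

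1. **10.2 and 10.4.** Replace the restriction with a statement that causality is assessed separately for (a) vitamin D, (b) the positive mood intervention and (c) study procedures, including study blood sampling, and that (c) applies in all four arms.
2. **Grade table in 10.2.** Reword the criteria so that the references to a study product and to other vaccines become references to the intervention or procedure being assessed. Without this, the 0 to 4 grades cannot be applied to a blood draw.
3. **Definitions in 10.1.** Align AE, AR and SAR so that they cover participants given no medicinal product and events due to study procedures. Changing the SAR definition alone would leave events that count as serious adverse reactions without fitting the definition of an adverse reaction.

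The cost is a protocol wording amendment, one extra field on the adverse event and SAE forms, and possibly a few more events labelled related. Sampling, treatment, eligibility and analysis stay as they are.
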